4.4.2 Blinding

Blinding will be accomplished by using a Treating Investigator to administer the treatments and a Blinded Evaluator, to whom randomization and treatment are concealed, to conduct the blinded assessments. The Treating Investigator will not be blinded. The Blinded Evaluator is not allowed to discuss treatments with the Treating Investigator or subjects. No study related documents that contain information regarding the treatment of subjects should be available to the Blinded Evaluator. Safety assessments will be performed by non-blinded personnel who are qualified by training and experience.

4.4.3 Emergency unblinding

Not applicable as the treating Investigator is not blinded to treatment.

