4.7.1 Visit 1, Screening (Day -30 to Day 1) - all subjects

The screening visit and baseline visit (Day 1) may be performed on the same day. The following activities and screening assessments will be performed within 30 days prior to baseline.

- o Obtain Informed Consent prior to conducting any study specific procedure.
- Assess eligibility: Review inclusion/exclusion criteria.
- Record the subject's medical history (including any prior dermatological procedures or implants).
- Record the subject's prior and concomitant therapies.
- Obtain demographic and baseline data: date of birth, height, weight, gender, ethnicity, race and Fitzpatrick Skin Type (FST).
 - FST is a skin classification system that categorizes different skin colors, and their reactions to ultraviolet light. (9, 10). For determination of the FST, see Table 3 below.
 - Height may be self-reported, weight is to be measured at clinic.
- Assess): Treating Investigator and Blinded Evaluator
- Perform safety assessments: Cheek sensation, Cheek firmness, symmetry and function, Mass formation
- Perform Visual Function Assessments (Snellen visual acuity, Extraocular muscle function and Confrontation visual field tests) for all subjects (prior to treatment for subjects in the treatment group).
- For all females of childbearing potential, perform Urine Pregnancy Test (UPT) prior to treatment. Test result must be negative for the subject to be eligible for treatment.
- Schedule the baseline and treatment visit (Day 1) if performed on a different day than screening.

The screening visit and baseline visit (Day 1) may be performed on the same day. If Screening visit and Baseline visit are not performed on the same day, the following should be repeated:

- Review for changes in concomitant therapies.
- o Re-confirm eligibility criteria
- o Obtain weight measured at clinic.

- Assess) Treating Investigator and Blinder Evaluator
- Perform Urine Pregnancy test for all females of childbearing potential (prior to treatment). Test result must be negative for the subject to be eligible for treatment.

Once the subject is deemed eligible by the Treating Investigator, the following procedures should be completed:

- Randomize the subject.
- Perform safety assessments: Cheek sensation, Cheek firmness, symmetry and function, Mass formation

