- 9. Treatment with chemotherapy, immunosuppressive agents (inhaled corticosteroids allowed), immunomodulatory therapy (e.g. monoclonal antibodies or antiviral treatment for HIV or Hepatitis C) within 6 months before treatment.
- 10. Use of topical corticosteroids or topical prescription retinoids (in the treatment area) within 1 month of the Baseline visit or systemic retinoid treatment within 6 months of the Baseline visit.
- 11. Previous surgery including plastic surgery, lifting threads, tissue grafting or tissue augmentation with permanent implants, silicone or fat, or tattoo, affecting the treatment area.
- 12. History of cancer or previous radiation near or on the area to be treated.
- 13. HIV positive or active hepatitis.
- 14. History of or active collagen diseases such as systemic lupus erythematosus, rheumatic arthritis, polymyositis, dermatomyositis, skin or systemic scleroderma.
- 15. Tendency to form keloids, hypertrophic scars, or any other healing disorder.
- 16. Presence of piercing, beard or facial hair that could interfere with study evaluation.
- 17. Abnormal result on functionality, sensation, symmetry, mass formation or palpation assessments in the treatment area.
- 18. Abnormal result on extraocular muscle function test or confrontational visual field assessment.
- 19. Presence of a dental, oral, or facial condition which, in the Treating Investigator's opinion, would interfere with the study injections and/or study assessment, e.g. has dentures or any device covering all or part of the upper palate, and/or severe malocclusion or dentofacial or maxillofacial deformities.
- 20. Woman who is pregnant (confirmed by positive urine pregnancy test/serum pregnancy test), breast-feeding or intend to become pregnant over the duration of the study.
- 21. Any medical condition that, in the opinion of the Treating Investigator, would make the subject unsuitable for inclusion (e.g. a chronic, relapsing or hereditary disease that may interfere with the outcome of the study).
- 22. Other condition preventing the subject from entering the study in the Treating Investigator's opinion, e.g. subjects failing baseline safety assessments, subjects not likely to avoid other

5.0

cosmetic treatments in the treatment area, subjects anticipated to be unavailable or incapable of understanding the study assessments or having unrealistic expectations of the treatment result.

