## 2.2.3 Safety Population

Includes all subjects who were treated with Sculptra Aesthetic or randomized to no treatment control group. Subjects are analyzed based on the as treated principle (i.e. according to the treatment actually received).

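### On different-day visits, the Day 1 cheek and visual tests follow randomization, so a new exclusion finding can surface only once the allocation is known

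*Protocol*

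**What the plan says.** The order of steps comes from the Protocol's visit descriptions (4.7.1 for screening, then the Day 1 list of 4.7.2).

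- **Screening**, up to 30 days before baseline, includes the cheek safety assessments and the visual function tests for every subject.
- **Day 1 on a different date** opens with "If Screening visit and Baseline visit are not performed on the same day, the following should be repeated". The repeated items are concomitant therapies, re-confirmation of eligibility, weight, the wrinkle score and the pregnancy test. No cheek or visual test is among them.
- **The gate** follows: "Once the subject is deemed eligible by the Treating Investigator, the following procedures should be completed". The first item under it is "Randomize the subject". Next comes "Perform safety assessments: Cheek sensation, Cheek firmness, symmetry and function, Mass formation", then the visual function tests, and later the injection.

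Tables 1 and 2 do not place these tests before randomization. Table 1 marks the eligibility check, randomization and the first set of visual tests only as pre-treatment. Footnote 1 says that assessments are not duplicated when both visits fall on one day.

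In 5.3, exclusion 17 concerns abnormal cheek assessments, and exclusion 18 reads "Abnormal result on extraocular muscle function test or confrontational visual field assessment". Neither names a visit. Exclusion 22, an investigator-opinion item, gives as an example "subjects failing baseline safety assessments". On who tests, 4.4.2 says "Safety assessments will be performed by non-blinded personnel who are qualified by training and experience", and it states that the Treating Investigator is not blinded.

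**The concern.** An exclusion criterion is meant to act before enrollment, and 5.4 and 8.6.5 tie enrollment to randomization or treatment. On different-day visits the baseline safety assessments named in exclusion 22 come after that point, so it cannot work as an enrollment criterion there. A subject who fails them is already randomized and cannot be a screen failure under 5.4. The people who read the result can know the arm.

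Two things are at stake. One is a decision with eligibility content taken after allocation. The other is a set of randomized but never injected subjects who can arise in one arm only and who drop out of that arm's safety tables.

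**Working it through.** **1. Which findings are affected.**

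| Case | Tests before randomization? | Gap? |
|---|---|---|
| Same-day visits | Yes: one set, listed under screening | No |
| Different days, abnormal at screening | Yes: exclusions 17 and 18 apply then | No |
| Different days, normal at screening, new or first detected on Day 1 | No | Yes |

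Only the last row is open.

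**2. What follows in each arm.** Protocol 6.5.2 says treatment is not performed in a subject with a disease or condition described in the exclusion criteria. Suppose an abnormal Day 1 test counts as one.

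| Consequence | Sculptra arm | Control arm |
|---|---|---|
| Injection withheld (6.5.2) | Yes | Cannot apply |
| In ITT (Protocol 10.2, SAP 2.2.1) | Stays | Stays |
| In the Safety population (SAP 2.2.3) | Out if never injected | Stays |
| Review as a possible adverse event (8.4.2, 8.4.3, 8.5) | Yes | Yes |
| Discretionary withdrawal (5.5), PP exclusion (10.2, 10.8) | Possible | Possible |

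The Safety row follows from the definition: "Includes all subjects who were treated with Sculptra Aesthetic or randomized to no treatment control group". A subject randomized to Sculptra and never injected meets neither condition. A mass first found on Day 1 is recorded as an adverse event in either arm (8.5.3, 8.6.5). It would be summarized for the control but not for the uninjected Sculptra subject.

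**3. The plan's own power figure.** Inputs from Protocol 10.9.3 and SAP 2.7: 70% against 35%, 84 and 42 evaluable subjects, two-sided 5%. SAP 2.4.4 names Fisher's exact test.

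- Stated power: approximately 90%.
- Recomputed: 97.0% (pooled z-test) and 95.7% (exact enumeration of Fisher's test). The stated figure is not reproduced. The difference is in the conservative direction and has no bearing on the order of procedures.
- Dropout: 126 / 0.85 = 148.2, rounded up to 149, which agrees with approximately 150.

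**4. Dilution.** Assume a barred subject stays in the study and responds at the control rate.

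Loss per barred subject in 100 = (70% − 35%) / 100 = 0.35 percentage points.

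For a share *f* of the Sculptra arm left uninjected, the arm's response rate is (1 − *f*) × 70% + *f* × 35%. The documents do not give *f*, so a range is shown. The last two columns count every barred subject as a non-responder, with rate (1 − *f*) × 70%. Power is exact Fisher at 84 and 42.

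| *f* (assumed) | Rate | Difference | Power | Rate, non-responders | Power, non-responders |
|---|---|---|---|---|---|
| 0 | 70.0% | 35.0 | 95.7% | 70.0% | 95.7% |
| 1% | 69.65% | 34.65 | 95.3% | 69.3% | 94.9% |
| 2% | 69.3% | 34.3 | 94.9% | 68.6% | 94.0% |
| 5% | 68.25% | 33.25 | 93.5% | 66.5% | 90.6% |
| 10% | 66.5% | 31.5 | 90.6% | 63.0% | 82.2% |

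**The case against.** The strongest reply is that eligibility is properly settled before randomization. Every subject has had the cheek and visual tests at screening, and re-confirming eligibility is a required step before the gate on Day 1. Exclusions 17 and 18 name no visit. Exclusion 22 is a catch-all, and the Protocol uses the word baseline loosely (8.5.3 speaks of screening and baseline together). The bullets are unnumbered, and the FACE-Q instruction appears twice, so list order alone is weak evidence.

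Much of this stands, and it rules out three stronger readings that a reader might infer:

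- *That exclusions 17 and 18 as a whole are read only after allocation.* They are not, because the screening tests come first.
- *That a control subject's abnormal result has no consequence.* Adverse event review, discretionary withdrawal and PP exclusion apply in both arms.
- *That subjects can be selected out of the primary analysis.* ITT keeps everyone as randomized, so what remains is dilution toward the null.

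It is also fair that 6.5.2 speaks of a disease or condition, while exclusions 17 and 18 speak of an abnormal result. Whether an isolated abnormal test stops injection is not stated.

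The reply does not remove the gap. The sentence that makes eligibility the gate, with randomization directly under it, carries the order without relying on the bullets. Re-confirming eligibility cannot use a Day 1 test that has not yet been done.

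**Conclusion.** The point holds in a narrow form and is of low severity. On different-day visits, exclusion 22 and any new abnormality under exclusions 17 or 18 can be found only after allocation, by staff who are not blinded to it. The one-arm effect is limited to withheld injection and the resulting absence from the Safety population. It depends on reading 6.5.2 as covering an abnormal test.

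For the primary analysis the cost is 0.35 percentage points per barred and retained subject in 100. At an assumed 2%, power goes from 95.7% to 94.9%. It falls below the planned level only in the harshest case shown, 10% barred and all counted as non-responders. These figures assume that barred subjects are retained and assessed at month 12, and neither the share of different-day visits nor the rate of new findings is in the documents. The case for acting rests on a usable exclusion criterion and matching safety sets, not on lost power.

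**What to change.** In 4.7.2, move the Day 1 cheek safety assessments and the pre-injection visual function tests into the list completed before the Treating Investigator declares eligibility and the subject is randomized. Footnote the randomization row of Tables 1 and 2 to say that it follows those tests.

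Reconcile 4.7.1, 4.7.2, Tables 1 and 2, exclusions 17, 18 and 22 in 5.3, and 6.5.2 on when these tests are done relative to randomization. The documents should also say whether an abnormal test falls under the 6.5.2 wording. That is a clinical question on which this point takes no view.

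The cost is a reordering within one visit, with no new procedure. The downside is a few minutes of testing in subjects who then fail on Day 1.

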4.7.11 Unscheduled Visits

- When necessary, unscheduled visits could take place (in particular because of an AE needing a specific treatment)
- \circ Unscheduled visits related to the study should be documented and all adverse events captured.

🖧 GALDERMA

5 Subjects

5.1 Subject information and informed consent

The PI or his/her authorized designee must always use the IRB-approved subject information and informed consent form and it must not be changed without prior discussion with the Sponsor and approval from the applicable IRB.

It is the responsibility of the PI or his/her authorized designee to give each subject prior to inclusion in the study, full and adequate verbal and written information regarding all aspects of the clinical study that are relevant to the subject's decision to participate throughout the study, e.g. explain the purpose and procedures of the study, the duration and number of expected participants, possible risks involved, and the opinion of the IRB. The subject shall be informed that the participation is confidential and voluntary and that the subject has the right to withdraw from the study at any time, without any consequences to his/her future medical care, treatment or benefits to which the subject is otherwise entitled. The information shall be provided in a language clearly and fully understandable to the subject. The subject shall be given sufficient time to read and understand the informed consent form and to consider participation in the study. Before any study-related activities are performed, the informed consent form shall be personally signed and dated by the subject and the PI or his/her authorized designee responsible for conducting the informed consent process. The consent includes information that data will be collected, recorded, processed, and may be transferred to other countries. The data will not contain any information that can be used to identify any subject.

Photographs collected during the study will be analyzed and stored in a database by the Sponsor and its representatives in order to evaluate the effect of the treatment in the study. The subjects will be recognizable on the photographs, but their names will not be disclosed.

All original signed informed consent forms shall be filed in the Investigator file. The subject shall be provided with a copy of the signed and dated informed consent form and any other written information.

The Investigator shall ensure that important new information is provided to new and existing subjects throughout the study.

5.2 Inclusion criteria

The subjects must meet the following criteria to be eligible for the study:

- 1. Subjects willing to comply with the requirements of the study and providing a signed written informed consent.
- 2. Women or men over 21 years of age.
- 3. Intent to undergo correction of cheek wrinkles on both sides of the face and a of Moderate or Severe on EACH side of the face, as assessed on Day 1 by the Blinded Evaluator as well as the Treating Investigator, but agreement on score is not required. The score for each side of the face does not need to be equal; however, the difference between the two sides should be limited to 1 grade.
- 4. Female subjects must be postmenopausal for at least 1 year; if the subject is a female of childbearing potential, she agrees to use an acceptable form of effective birth control for the duration of the study and is willing to take a urine pregnancy test at the screening visit and prior to all injection visits. Acceptable forms of effective birth control methods include:
 - a. Combined oral contraceptives (estrogens and progesterone) or implanted or injectable contraceptives with a stable dose for at least 28 days prior to the Baseline visit
 - b. Hormonal or copper intrauterine device (IUD) inserted at least 28 days prior to the Baseline visit

- c. Barrier methods of contraception: condom or occlusive cap (diaphragm or cervical caps) with spermicidal foam/gel/film/cream/suppository
- d. Bilateral tubal ligation prior to the Baseline visit
- e. Vasectomized partner (in monogamous relationships) for at least 3 months prior to the Baseline visit
- f. Strict abstinence (at least one month prior to baseline and agrees to continue for the duration of the study or use acceptable form of birth control).

5.3 Exclusion criteria

The presence of any of the following exclusion criteria will exclude a subject from enrollment in the study:

- 1. Known/previous allergy or hypersensitivity to any of the Sculptra Aesthetic constituents.
- 2. Known/previous allergy or hypersensitivity to lidocaine and other local anesthetics, e.g. amidetype anesthetics or topical anesthetics agents.
- 3. Previous or present multiple allergies or severe allergies, such as manifested by anaphylaxis or angioedema, or family history of these conditions.
- 4. Previous tissue augmenting therapy, contouring or revitalization treatment in the face, except the lips, with any of the following filler prior to Baseline visit:
 - a. Collagen, Hyaluronic Acid 12 months
 - b. Calcium Hydroxyapatite (CaHa), Poly L- Lactic Acid (PLLA) or permanent (nonbiodegradable)- Prohibited
- 5. Previous treatment/procedure in the face in the previous 6 months that, in the Treating Investigator's opinion, would interfere with the study injections and/or study assessments or exposes the study subject to undue risk by study participation, e.g.:
 - a. Resurfacing (laser, photomodulation, light, radiofrequency, ultrasound, chemical peel, dermabrasion, or other ablative/non- ablative procedures)
 - b. Needling or mesotherapy
 - c. Cryotherapy
 - d. Neurotoxin injections
 - e. Lipolytic injections (e.g. dexycholic acid or other lipolytic substances)
 - f. Dental work, such as root canals or sinus surgery

or is planning to undergo any of these procedures affecting the treatment area, at any time during the study.

- 6. Presence of any disease or lesions near or on the area to be treated, e.g.
 - a. Inflammation, active or chronic infection in or near the treatment area

- b. Facial psoriasis, eczema, acne, rosacea, perioral dermatitis, herpes zoster/ herpes simplex and acanthosis
- c. Scars or deformities
- d. Cancer or precancerous condition (e.g. actinic keratosis or actinic cheilitis)
- 7. History of severe elastosis and/or excessive sun exposure that in the opinion of the Treating Investigator, could affect the safety and effectiveness outcome of the study.
- 8. History of bleeding disorders or treatment with anticoagulants or inhibitors of platelet aggregation (e.g. aspirin or other NSAIDs), Omega-3, or vitamin E within 14 days before treatment. Omega 3 and Vitamin E are acceptable only as part of a standard multivitamin formulation.
- 9. Treatment with chemotherapy, immunosuppressive agents (inhaled corticosteroids allowed), immunomodulatory therapy (e.g. monoclonal antibodies or antiviral treatment for HIV or Hepatitis C) within 6 months before treatment.
- 10. Use of topical corticosteroids or topical prescription retinoids (in the treatment area) within 1 month of the Baseline visit or systemic retinoid treatment within 6 months of the Baseline visit.
- 11. Previous surgery including plastic surgery, lifting threads, tissue grafting or tissue augmentation with permanent implants, silicone or fat, or tattoo, affecting the treatment area.
- 12. History of cancer or previous radiation near or on the area to be treated.
- 13. HIV positive or active hepatitis.
- 14. History of or active collagen diseases such as systemic lupus erythematosus, rheumatic arthritis, polymyositis, dermatomyositis, skin or systemic scleroderma.
- 15. Tendency to form keloids, hypertrophic scars, or any other healing disorder.
- 16. Presence of piercing, beard or facial hair that could interfere with study evaluation.
- 17. Abnormal result on functionality, sensation, symmetry, mass formation or palpation assessments in the treatment area.
- 18. Abnormal result on extraocular muscle function test or confrontational visual field assessment.
- 19. Presence of a dental, oral, or facial condition which, in the Treating Investigator's opinion, would interfere with the study injections and/or study assessment, e.g. has dentures or any device covering all or part of the upper palate, and/or severe malocclusion or dentofacial or maxillofacial deformities.
- 20. Woman who is pregnant (confirmed by positive urine pregnancy test/serum pregnancy test), breast-feeding or intend to become pregnant over the duration of the study.
- 21. Any medical condition that, in the opinion of the Treating Investigator, would make the subject unsuitable for inclusion (e.g. a chronic, relapsing or hereditary disease that may interfere with the outcome of the study).
- 22. Other condition preventing the subject from entering the study in the Treating Investigator's opinion, e.g. subjects failing baseline safety assessments, subjects not likely to avoid other

5.0

cosmetic treatments in the treatment area, subjects anticipated to be unavailable or incapable of understanding the study assessments or having unrealistic expectations of the treatment result.

- 23. Study site personnel, close relatives of the study site personnel (e.g. parents, children, siblings, or spouse), or employees and close relatives of employees at the Sponsor company.
- 24. Participation in any interventional clinical study within 30 days of screening.

5.4 Subject number

Prior to any study procedures being conducted, the subject must sign the informed consent form. Each subject who has signed the informed consent form will be assigned a screening number. Upon randomization, each subject will be assigned a subject numbers that will be allocated in ascending order within each center. A screen failure is a subject who signed the informed consent but never enrolled (i.e. was randomized and/or received treatment) in the study. For screen failures, the subject source documents should indicate which assessments have been made and the reason why the subject was determined to be a screen failure. A screen failure should not be re-entered in the study.

For the duration of the clinical study, each subject will be identified using the subject number for all documentation and discussion.

